8.1 General Conventions

Subject data will be summarized in tables and presented in further detail in listings. All eCRF data will be listed per subject for all subjects. Descriptive statistical analyses will be provided for pre-specified study endpoints. Summaries for continuous variables will include a minimum of number of observations (n), mean, standard deviation, median, minimum and maximum. Summaries for categorical variables will include number and frequency.

Analyses will be conducted using SAS software. During the course of programming of tables that are mocked up in this SAP, minor modifications may become necessary. Examples of these minor modifications include, but are not limited to, table title, re-wording of a footnote, addition of a footnote, re-labeling of a column, or addition or removal of a column from a listing. In cases where modifications to tables or listings are not related to a change in statistical analysis methodology or conclusions that could be made on the originally proposed methodology, then no amendment of the SAP is necessary. Any final analyses that differ from what has been specified in this document will be identified within the final statistical output and documented within the clinical study report.

8.2 Disposition of Study Subjects

Subject disposition will be summarized using counts and percentages. The number and percentage of subjects in the Full Analysis Set (FAS) who completed and withdrawal will be tabulated along with the specific reasons for withdrawal.

8.3 Demographic, and other Baseline Characteristics

Demographic and other baseline characteristics will be summarized descriptively for subjects in the FAS.

The following demographic variables will be summarized:

- Age
- Gender
- Race
- Height
- Weight
- Body Mass Index (BMI) at baseline
- Ethnicity

8.4 Surgical Characteristics

Basic surgical characteristics will be summarized using count and frequency.

The following variables will be summarized:

- Documentation of LSG and GERD History (time had GERD, PPI taking history, GERD status, duration between LSG surgery and LINX surgery, and BMI at time of LINX surgery).
- Implantation, including surgical duration, device size, concomitant surgical procedure, and perioperative complications.

8.5 Efficacy

Efficacy will be measured by a comparison of GERD control before and after placement of the LINX Reflux Management System defined by esophageal pH measurements, GERD-HRQL score and PPI use. The change from baseline by follow-up will be calculated and summarized.

8.5.1 Esophageal Acid Exposure

Testing will be performed with subjects off PPIs. The subject's total distal esophageal acid exposure time at baseline will serve as the control and will be compared to results at the 12-month visit. Normalization for total distal ambulatory esophageal pH testing is defined as pH < 4 for < 4.5% of the time. If longer pH evaluations are received, the total distal acid exposure time will be recorded as a 24-hour average (e.g. 48-hour Bravo testing).

The proportion of subjects achieving pH normalization or at least a >50% reduction from baseline to the result at the 12-months will be summarized descriptively for the FAS. Two-sided 95% CI will also be constructed using exact Clopper-Pearson method.

8.5.2 Quality of Life

Subjects GERD-HRQL (Health Related Quality of Life) scores will be assessed off all GERD medications. The subject's baseline GERD-HRQL score will serve as the control and be compared to the subject's GERD-HRQL 12 months post implantation.

Summary statistics will be provided for the GERD-HRQL questionnaire. Subjects are asked to rate 10 specific symptoms in addition to assessing how satisfied they are with their present condition. Each symptom is scored on a 0 to 5 scale. Summaries will also be provided for an overall score which is calculated as the average of the ten components for each subject.

Counts and percentages will be provided for responses to the GERD-HRQL questionnaire.

8.5.3 Use of PPIs

Subject's average daily dose of PPI will be evaluated. The subject's baseline average daily dosage will serve as the control and be compared to the subject's average daily dosage 12 months post-procedure.

The proportion of subjects with at least 50% reduction in daily PPI use from baseline at 12 months will be reported. In addition, a two-sided 95% CI will be provided for the proportion of success (>=50% reduction achieved).

8.6 Safety Analyses

Safety will be assessed by the rate of AEs and SAEs (number and percentage of subjects experiencing). Similar summaries will also be provided for AEs and SAEs related to the study device, as well as for AEs and SAEs related to the study procedures. Related events are those where the event relatedness is indicated as Yes/Probably/Possibly, or Unknown. Esophageal anatomy and functionality will be monitored by performing manometry and barium esophagram at 12-months post-implant. A summary and change from baseline of manometry and motility results will be provided which includes LES length, LES residual pressure, LES intra-abdominal length, LES basal mean pressure, percent peristaltic sequences, distal amplitude, distal contractile integral, percent ineffective swallows, and percent fragmented swallow. Count and percentages will be provided for barium esophagram in the number of subjects who have normal swallow function, number of subjects who have a dilated proximal pouch, number of subjects who have evidence of a hiatal hernia, and if any abnormalities occurred. This will allow for identification of any abnormal or atypical findings. Further, device migration will be assessed by confirming device position at the GEJ by obtaining upright, bi-plane X-rays and device erosion will be assessed by performing an endoscopy at the 12 months visit.

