6.2 EXCLUSION CRITERIA

Subjects should be excluded from the study based on the following criteria:

1. The procedure is an emergency procedure.
2. Suspected or known allergies to titanium, stainless steel, nickel, or ferrous materials.
3. Presence of >3 cm hiatal hernia as determined by endoscopy or barium esophagram.
4. Subject had any major complications related to the laparoscopic sleeve gastrectomy that may interfere with, or increase the risks of the LINX procedure (such as, but not limited to, leaks from the gastric remnant and infection at the sleeve gastrectomy)
5. Plans to surgically revise the gastric pouch (either known preoperatively or decided intraoperatively)
6. Currently being treated with another investigational drug or investigational device.
7. Suspected or confirmed esophageal or gastric cancer or prior gastric or esophageal surgery or endoscopic intervention for GERD (with the exception of sleeve gastrectomy).
8. Distal amplitude <35 mmHg or <70% peristaltic sequences (if using Conventional Manometry)

-or-

If using High Resolution Manometry (exclude for any of the following):

- Distal Contractile Integral (DCI) ≤ 450 mmHg·s·cm or
- $\geq 50\%$ ineffective swallows or
- $\geq 50\%$ fragmented swallows

(Fragmented swallows are defined as those with a ≥ 5 cm break [large] in peristaltic integrity)

9. Presence of esophagitis – Grade C or D (LA Classification).
10. BMI >35.
11. Symptoms of dysphagia more than once per week within the last 3 months.
12. Diagnosed with Scleroderma.
13. Diagnosed with an esophageal motility disorder such as but not limited to achalasia, nutcracker esophagus, or diffuse esophageal spasm or hypertensive LES.
14. Subject has a history of or known esophageal stricture or gross esophageal anatomic abnormalities (Schatzki's ring, obstructive lesions, etc.)
15. Subject has esophageal or gastric varices
16. History of/or known Barrett's esophagus.
*Note: The diagnosis of Barrett's esophagus requires both **endoscopic** and **histologic** evidence of metaplastic columnar epithelium. Endoscopically, there must be columnar epithelium within the esophagus. Histologically, the epithelium must be metaplastic, as defined by the presence of goblet cells.*
17. Subject cannot understand trial requirements or is unable to comply with follow-up schedule
18. Pregnant or nursing, or plans to become pregnant during the course of the study.

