Parameter	Baseline	12 Months Follow-Up	Change from Baseline to 12 Months Follow-Up
Daily Average of DeMeester Score			
n	xx	xx	xx
Mean (SD)	xx.x (xx.x)	xx.x (xx.x)	xx.x (xx.x)
Median (Min, Max)	xx.x (xx, xx)	xx.x (xx, xx)	xx.x (xx, xx)
Number of Subjects with Normal DeMeester Score based on Daily Average (≤ 14.72)	xx (xx.x%)	xx (xx.x%)	xx (xx.x%)

Note: For all parameters, the within subject average of the values within a visit is first calculated prior to summarizing across all subjects at the given visit. Subjects with simultaneous zero as pH measurements are not included in daily average calculation.

<Programming Note: Records with all pH parameters: reflux episodes (PHRESRE), reflux episodes > 5 min (PHRESREM), longest episode (PHRESLE), total % time (PHRESTT), upright % time (PHRESUT), supine % time (PHRESST) and DeMeester score (PHRESDS) as zero, should be excluded in daily average calculation.>

Table 8
Summary of Manometry/Motility Results
Full Analysis Set

Characteristic	Baseline	12 Months Follow-Up	Change from Baseline to 12 Months Follow-Up
LES Length (cm)			
n	xx	xx	xx
Mean (SD)	xx.x (xx.x)	xx.x (xx.x)	xx.x (xx.x)
Median (Min, Max)	xx.x (xx, xx)	xx.x (xx, xx)	xx.x (xx, xx)
LES Residual Pressure (mmHg)			
n	xx	xx	xx
Mean (SD)	xx.x (xx.x)	xx.x (xx.x)	xx.x (xx.x)
Median (Min, Max)	xx.x (xx, xx)	xx.x (xx, xx)	xx.x (xx, xx)
LES Intra-Abdominal Length (cm)			
n	xx	xx	xx
Mean (SD)	xx.x (xx.x)	xx.x (xx.x)	xx.x (xx.x)
Median (Min, Max)	xx.x (xx, xx)	xx.x (xx, xx)	xx.x (xx, xx)
LES Basal Mean Pressure (mmHg)			
n	xx	xx	xx
Mean (SD)	xx.x (xx.x)	xx.x (xx.x)	xx.x (xx.x)
Median (Min, Max)	xx.x (xx, xx)	xx.x (xx, xx)	xx.x (xx, xx)
Percent Peristaltic Sequences (%)			
n	xx	xx	xx
Mean (SD)	xx.x (xx.x)	xx.x (xx.x)	xx.x (xx.x)
Median (Min, Max)	xx.x (xx, xx)	xx.x (xx, xx)	xx.x (xx, xx)
Distal Amplitude (mmHg)			
n	xx	xx	xx
Mean (SD)	xx.x (xx.x)	xx.x (xx.x)	xx.x (xx.x)
Median (Min, Max)	xx.x (xx, xx)	xx.x (xx, xx)	xx.x (xx, xx)
Distal Contractile Integral (mmHg·s·cm)			
n	xx	xx	xx
Mean (SD)	xx.x (xx.x)	xx.x (xx.x)	xx.x (xx.x)
Median (Min, Max)	xx.x (xx, xx)	xx.x (xx, xx)	xx.x (xx, xx)
Percent Ineffective Swallows (%)			
n	xx	xx	xx
Mean (SD)	xx.x (xx.x)	xx.x (xx.x)	xx.x (xx.x)
Median (Min, Max)	xx.x (xx, xx)	xx.x (xx, xx)	xx.x (xx, xx)

Table 8
 Summary of Manometry/Motility Results
 Full Analysis Set

Characteristic	Baseline	12 Months Follow-Up	Change from Baseline to 12 Months Follow-Up
Percent Fragmented Swallows (%)			
n	xx	xx	xx

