<Programming note: Only device size and concomitant surgical procedures observed need be displayed. Length of stay is defined as discharge date (from discharge page) minus hospital admission date. >

Table 11
Barium Esophagram Summary
Full Analysis Set

Characteristic	Baseline (N = ##)	Implant/Discharge (N = ##)	12 Months Follow-Up (N = ##)
Number of subjects have normal swallow function	xx (xx.x%)	xx (xx.x%)	xx (xx.x%)
Number of subjects have a dilated proximal pouch	xx (xx.x%)		xx (xx.x%)
Number of subjects have evidence of a hiatal hernia	xx (xx.x%)		xx (xx.x%)
Any Abnormalities?			
Yes	xx (xx.x%)	xx (xx.x%)	
No	xx (xx.x%)	xx (xx.x%)	

Denominator and percentages are based on subjects with non-missing data.

Table 12
Summary of GERD-HRQL Questionnaire at Baseline (On PPI)
Full Analysis Set

Characteristic	Baseline
Number of Subjects Completed Questionnaires per Protocol Requirements	xx
How bad is your heartburn?	
0 - No symptoms	xx (xx.x%)
1 - Symptoms noticeable, but not bothersome	xx (xx.x%)
2 - Symptoms noticeable and bothersome, but not every day	xx (xx.x%)
3 – Symptoms bothersome every day	xx (xx.x%)
4 – symptoms affect daily activities	xx (xx.x%)
5 – Symptoms are incapacitating, unable to do activities	xx (xx.x%)
Heartburn when lying down?	
0 - No symptoms	xx (xx.x%)
1 - Symptoms noticeable, but not bothersome	xx (xx.x%)
2 - Symptoms noticeable and bothersome, but not every day	xx (xx.x%)
3 – Symptoms bothersome every day	xx (xx.x%)
4 – symptoms affect daily activities	xx (xx.x%)
5 – Symptoms are incapacitating, unable to do activities	xx (xx.x%)
Heartburn when standing up?	
0 - No symptoms	xx (xx.x%)
1 - Symptoms noticeable, but not bothersome	xx (xx.x%)
2 - Symptoms noticeable and bothersome, but not every day	xx (xx.x%)
3 – Symptoms bothersome every day	xx (xx.x%)
4 – symptoms affect daily activities	xx (xx.x%)
5 – Symptoms are incapacitating, unable to do activities	xx (xx.x%)
Heartburn after meals?	
0 - No symptoms	xx (xx.x%)
1 - Symptoms noticeable, but not bothersome	xx (xx.x%)
2 - Symptoms noticeable and bothersome, but not every day	xx (xx.x%)
3 – Symptoms bothersome every day	xx (xx.x%)
4 – symptoms affect daily activities	xx (xx.x%)
5 – Symptoms are incapacitating, unable to do activities	xx (xx.x%)

Denominator and percentages are based on subjects completed questionnaires per protocol requirements.

Table 12
 Summary of GERD-HRQL Questionnaire at Baseline (On PPI)
 Full Analysis Set

Characteristic	Baseline

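### Manometry and barium results are planned without a count of subjects who move from normal to abnormal, so the rate of worsening must be pieced together from the listings

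*SAP*

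**What the plan says.** Sections 5.1 and 10.2 of the protocol place esophageal anatomy and function at 12 months under safety, to be followed by manometry and barium esophagram. Section 8.6 of the SAP sets out the analysis.

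- **Manometry:** "A summary and change from baseline of manometry and motility results will be provided". Table 8 ("Summary of Manometry/Motility Results") gives n, mean (SD) and median (min, max) for nine parameters at baseline, at 12 months and for the change. It has no categorical row and no row for the manometry method.
- **Barium:** "Count and percentages will be provided for barium esophagram in the number of subjects who have normal swallow function", and likewise for a dilated pouch, a hernia and any abnormality. The Table 11 footnote reads: "Denominator and percentages are based on subjects with non-missing data".
- **Stated aim:** after describing these summaries, section 8.6 says: "This will allow for identification of any abnormal or atypical findings".

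Three other places bear on the point.

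- Exclusion 8 in protocol section 6.2 sets motility limits by method. For conventional manometry they are distal amplitude under 35 mmHg or under 70% peristaltic sequences. For high-resolution manometry they are a distal contractile integral (DCI) of 450 or less, or at least 50% ineffective or 50% fragmented swallows.
- Exclusion 3 removes only the larger hernias: "Presence of >3 cm hiatal hernia as determined by endoscopy or barium esophagram".
- Table 9 of the SAP classes the change in esophagitis grade as improved, unchanged or worse, among subjects evaluated at both visits.

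**The concern.** The device encircles the lower esophagus, and the study is meant to support a labeling statement on safety after sleeve gastrectomy. A reader of the report will want to know how many subjects had adequate motility or a normal swallow before the implant and did not have it a year later. The planned tables do not give that number.

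For manometry, nothing says what makes a 12-month result abnormal, although the protocol used explicit limits at entry. For barium, percentages at two visits on different sets of subjects give only a net difference. Findings that resolve and findings that appear cancel out, and so may differences in who came back. Hernias of up to 3 cm may be present at entry, and hernia repair at implant is a listed concomitant procedure, so movement in both directions is plausible.

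Unequal denominators are also likely. SAP 8.8 reports lower follow-up than anticipated, and SAP 8.9 uses observed data only.

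**Working it through.** The documents give no abnormality rate, margin or sample size calculation for this point, so there is no planned figure to reproduce. Every count below is an assumption chosen to show what the tables can and cannot convey.

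**1. The shells side by side**

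| Assessment | Abnormality defined? | Subjects counted? | Paired change of status? |
|---|---|---|---|
| Manometry (Table 8) | No | No | No; the change is paired, but continuous |
| Barium (Table 11) | By finding | Yes, per visit | No |
| Esophagitis (Table 9) | By grade | Yes | Yes |

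**2. Manometry**

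Assume 20 subjects with high-resolution results at both visits. Four fall in DCI from 1500 to 400 (change −1100), and 16 rise by 275.

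- Mean change = (4 × (−1100) + 16 × 275)/20 = (−4400 + 4400)/20 = 0.
- SD of change = √[(4 × 1100² + 16 × 275²)/19] = √(6,050,000/19) ≈ 564.
- Median change = +275; minimum −1100; maximum +275. The 12-month minimum is at most 400.
- Subjects newly at or below 450: 4/20 = 20%, Clopper-Pearson 95% CI 5.7% to 43.7%, assuming the other 16 stay above it.

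The mean and median suggest no loss. The SD and minimum reveal a bad tail, and the 12-month minimum shows that at least one subject crossed 450. No entry says that four did.

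A milder pattern: 3 of 30 fall from 1500 to 300 and the rest are unchanged. Mean change = 3 × (−1200)/30 = −120, median change 0, 12-month minimum 300. Again the table shows at least one subject below the limit, but not how many.

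**3. Barium**

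Let b subjects be abnormal at baseline and a at 12 months, with the same n examined at both. The number newly abnormal lies between max(0, a − b) and min(a, n − b).

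- For n = 30 and a = b = 6: from max(0, 0) = 0 to min(6, 24) = 6, that is 0% to 20%. The exact 95% CI is 0% to 11.6% at one end (0/30) and 7.7% to 38.6% at the other (6/30).

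With unequal denominators, suppose 6/30 are abnormal at baseline and 4/20 at 12 months, both 20%, and all 20 had a baseline examination. Let k be the number of those 20 who were abnormal at baseline. As 10 subjects are missing at 12 months, k can be anything from max(0, 6 − 10) = 0 to 6.

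- Fewest new: max(0, 4 − k) = 0 when k is 4 or more.
- Most new: min(4, 20 − k) = 4.

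Two identical percentages are therefore compatible with 0 to 4 new findings among 20 subjects.

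**4. What a paired count would show**

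With no events, the exact upper 95% limit is 1 − 0.025^(1/n).

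| Paired subjects | Upper limit when 0 are newly abnormal |
|---|---|
| 30 | 11.6% |
| 20 | 16.8% |
| 15 (30 subjects split 50:50 by method) | 21.8% |
| 6 (smaller group, 30 split 80:20) | 45.9% |

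The split by method is assumed, because the documents do not give the mix.

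**The case against.** The strongest reply is that the plan already exposes individual results. SAP 8.1 lists all case report form data by subject. Listing 6 covers manometry and Listing 9 barium. With at most 30 subjects, both visits can be read directly. Table 8 also reports SD, median and range, with the change computed within subject. In the first manometry example it would show a minimum change of −1100. This stands: a reader might infer that the plan cannot find abnormal subjects, or that Table 8 would report no change while several worsen, and neither is right.

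Two further stronger readings also fail.

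- A reader might take section 8.6 to promise detection of newly abnormal function. It speaks of abnormal findings. In protocol 5.1 and 10.2 the same sentence follows the description of the tests themselves.
- A reader might infer that no row of Table 8 covers both manometry methods. Exclusion 8 ties five of the nine parameters to a method, and only for entry. The four sphincter parameters are tied to none, and nothing says that amplitude or peristalsis goes unreported under high-resolution testing.

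It is also fair to say that exclusion 8 holds selection limits, not a definition of post-implant abnormality, and that the two sets of limits are not stated to be equivalent. This shapes the fix but does not remove the gap. A listing without a criterion fixed in advance leaves the decision on what is abnormal until the data are seen, and yields no rate or interval. The SAP itself found a paired count worth planning for esophagitis.

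**Conclusion.** The point holds as a limited gap in reporting. Table 8 has no criterion for abnormal motility and no count of subjects. Table 11 has no paired row. The number and rate of subjects moving from normal to abnormal would therefore not appear in the report, although they can be derived from data already collected. Table 11 does count some abnormal findings at 12 months; what it lacks is whether they are new.

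For motility, subjects who truly met exclusion 8 were within the limits at entry, so a 12-month result outside them would be new. The baseline condition should still be checked, because SAP section 6 identifies the analysis set by the answer on implantation, which would not screen out an eligibility deviation. For barium, pairing matters more, since abnormal findings are allowed at entry.

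The size rests on assumed counts: 0 to 6 new findings among 30 behind identical barium percentages, or 4 of 20 losing motility behind a zero mean change. The true figures may be far smaller.

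Two limits apply. Some table shells after Table 21 and the manometry guideline in Appendix B were not available, although section 8.6 describes no such count. The 12-month cell for any abnormality in Table 11 may be misplaced in the extracted text and is not relied on. The importance is minor, and the efficacy endpoints are untouched.

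**What to change.** 1. **Table 8.** Add the number and percentage, with exact 95% CI, of subjects tested at both visits who were within the exclusion 8 limits at baseline and outside them at 12 months. Judge each result by the method used at that visit. Show the count by method and then combined, and flag subjects whose method changed. The protocol's request to keep the same equipment appears under pH testing (section 10.1.1), and a subject who switches method may have no change value for some parameters. Label the limits as a descriptive reference taken from the entry criteria, not as a clinical rule.
2. **Table 11.** Among subjects examined at both visits, add paired rows with exact 95% CIs: normal swallow function at baseline and not normal at 12 months, new dilated pouch, and new hiatal hernia.

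The cost is a little programming on data already collected; no hypothesis or new assessment is involved. The drawbacks are small denominators within each method, hence wide intervals, and entry limits that serve only as a yardstick for function after implant.

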8.7 Additional Analyses

- Summary statistics will be provided for components of the DeMeester score at 12 months, which includes total % time, upright % time, supine % time, reflux episodes, reflux episodes > 5 min, and longest episode (min). For each of the individual components listed above as well as the overall DeMeester score, the average within a subject will first be calculated given that the number of days reported for each subject varies between 1 and 4. The 'Total' value reported in the database will not be utilized, and the average score for each parameter at each visit will be summarized in the overall value.
- Counts and percentages will be presented for subjects who discontinue daily PPI use at 3, 6 and 12 months.
- Counts and percentages will be provided for subjects with esophagitis by endoscopy at 12 months (using L.A. Classification). Additional endoscopic results provided will include: evidence of device erosion, hiatal hernia size and gastroesophageal junction morphology using Hill Grade. Summary statistics will also be provided for hiatal hernia size.

- Counts and percentages for responses to the Foregut Symptoms Questionnaire (FSQ) will be provided for subjects who meet the following criteria at 3, 6, and 12 months.
 - Subjects who eliminate moderate or severe regurgitation
 - Subjects with extra-esophageal symptoms or lung problems (Recurrent cough, Nocturnal cough, Recurrent Pneumonitis, Asthma, and Change of voice)
 - Subjects with ability to belch
 - Subjects with ability to vomit

